8.3.3.2. Dosing Rechallenge and Premedication for Infusions

Donanemab

Premedication for dosing is not planned. Dosing rechallenge is contraindicated in participants that have experienced a suspected or possible anaphylactic reaction (for example, reaction involving 2 or more organ systems [for example, mucocutaneous, respiratory, cardiovascular, or gastrointestinal systems] occurring in close proximity to dosing), in a prior dose (Sampson et al. 2006). For infusion-related reactions which are not suspicious for anaphylaxis, at the investigator's discretion, the participant may continue to receive study intervention. The participant may be premedicated for subsequent doses at investigator's discretion and according to local practice guidelines. Any premedication given will be documented as a concomitant therapy (Section 6.8).

Aducanumab

Investigators should consult the product label and follow local practice.

8.3.4. Adverse Events of Special Interest

Specific safety topics of interest for this study include, but are not limited to, the following:

- ARIA-E
- ARIA-H
- Hypersensitivity, immediate and non-immediate, including infusion-related reactions and anaphylaxis

The topics listed above, as well as other topics which may be subsequently determined by the sponsor, will be subject to enhanced surveillance activities. Additionally, the topics above will be analyzed for presentation in the Clinical Study Report in accordance with the SAP.

8.4. Pharmacokinetics

- a. Serum samples will be collected for measurement of serum concentrations of study intervention as specified in the SoA.
- b. The timing of sampling may be altered during the course of the study based on newly available data (e.g., to obtain data closer to the time of peak plasma concentrations) to ensure appropriate monitoring.
- c. Instructions for the collection and handling of biological samples will be provided by the sponsor. The actual date and time (24-hour clock time) of each sample will be recorded.
- d. Bioanalytical samples collected to measure study intervention will be retained for a maximum of 1 year following last participant visit for the study. During this time, samples remaining after the bioanalyses may be used for exploratory analyses such as metabolism, protein binding, or bioanalytical method development/validation work.

8.5. Pharmacodynamics

Pharmacodynamic parameters are not evaluated in this study.

8.6. Genetics

8.6.1. Apolipoprotein E Genotyping

ApoE genotyping is a mandatory part of this study. Blood sampling for ApoE genotyping will be performed as shown in the SoA. Neither participants nor investigators will receive the genotype results unless there is a country-specific law or regulation that requires notification of the results.

8.6.2. Whole Blood Samples for Pharmacogenetic Research

A blood sample for DNA isolation will be collected from participants.

See Appendix 5, Section 10.5 for information regarding genetic research and Appendix 1, Section 10.1.12 for details about sample retention and custody.

8.7. Biomarkers

Biomarker research is performed to address questions of relevance to drug disposition, target engagement, PD, mechanism of action, variability of participant response (including safety), and clinical outcome. Sample collection is incorporated into clinical studies to enable examination of these questions through measurement of biomolecules including proteins, lipids, and other cellular elements.

Serum and plasma, samples for biomarker research will be collected at the times specified in the SoA (Section 1.3) where local regulations allow.

Samples will be used for research on the drug target, disease process, variable response to study intervention, pathways associated with AD, mechanism of action of study intervention, and/or research method or in validating diagnostic tools or assay(s) related to AD or other neurological conditions.

All samples will be coded with the participant number. These samples and any data generated can be linked back to the participant only by the investigator site personnel.

Samples will be retained per Section 10.1.12.

8.8. Immunogenicity Assessments

At the visits and times specified in the SoA (Section 1.3), venous blood samples will be collected to determine antibody production against donanemab. Antibodies may be further characterized and/or evaluated for their ability to neutralize the activity of donanemab. To interpret the results of immunogenicity, a venous blood sample will be collected at the same time points to determine the serum concentrations of donanemab. All samples for immunogenicity should be taken predose when applicable and possible.

Immunogenicity will be assessed by a validated assay designed to detect ADAs in the presence of donanemab at a laboratory approved by the sponsor.

Treatment-emergent ADAs are defined in Section 9.3.6.2. If the immunogenicity sample at the last scheduled assessment or discontinuation visit is TE ADA positive, additional samples may be taken for up to approximately 1 year after last dose.

Samples will be retained per Section 10.1.12.

8.9. Health Economics

Health economics or medical resource utilization and health economics parameters are not evaluated in this study.

9. Statistical Considerations

The SAP will be finalized prior to first participant visit, and it will include a more technical and detailed description of the statistical analyses described in this section. This section is a summary of the planned statistical analyses of the most important endpoints, including primary and key secondary endpoints.

9.1. Statistical Hypotheses

The primary objectives of this study are to demonstrate that donanemab is superior to aducanumab in achieving complete brain amyloid plaque clearance at 6 months in the overall population and the intermediate tau subpopulation. These two objectives will be considered as co-primary, with the 6-month test occurring when all participants have had a chance to receive their 6-month amyloid PET scan.

The parameters of interest for the primary analyses (for both ITT and the intermediate tau subpopulation) are:

- $p_{\text{dona},6\text{m}}$: the probability that a participant will achieve complete brain amyloid clearance at 6 months under the donanemab treatment regimen.
- $p_{\text{adu},6\text{m}}$: the probability that a participant will achieve complete brain amyloid clearance at 6 months under the aducanumab treatment regimen.

$$\text{Odds ratio: } OR_{6\text{m}} = [(p_{\text{dona},6\text{m}})/(1 - p_{\text{dona},6\text{m}})]/[(p_{\text{adu},6\text{m}})/(1 - p_{\text{adu},6\text{m}})]$$

The null and alternative (1-sided) hypotheses to be tested are:

- H_0 : $OR_{6\text{m}} = 1$
- H_A : $OR_{6\text{m}} > 1$

The odds ratio for the overall population and for the intermediate tau subpopulation will be estimated using logistic regression models as described in Section 9.3. The analyses of the two primary end points and the key secondary endpoints will be controlled to be under a 2-sided Type 1 error rate of 5%, or equivalently, a 1-sided rate of 2.5%. The details regarding the testing scheme for these analyses will be described in the SAP.

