9.3.3. Primary Analyses

Proportion of Participants with Amyloid Plaque Clearance at 6 months

The primary objective of this study is to test the hypothesis that participants treated with donanemab will have a significantly greater proportion of participants who reach amyloid plaque clearance compared to participants treated with aducanumab at the 6-month timepoint in both the ITT population and the intermediate tau subpopulation.

As the 6-month timepoint is the first scheduled opportunity to collect a post-baseline florbetapir F18 PET scan, the comparison of donanemab to aducanumab in complete brain amyloid clearance at 6 months will be performed using logistic regression. The logistic regression model will include fixed effect for treatment, ApoE ϵ 4 genotype, and baseline amyloid level. The test for this endpoint will be based on the contrast for the main effect of treatment from this logistic regression model. Treatment effects will be presented using odds ratios and 95% confidence intervals. This analysis will be conducted on the full ITT population and the intermediate tau subpopulation.

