The primary clinical question of interest is: What is the difference in brain amyloid plaque clearance after 6 months of intervention in participants with early symptomatic Alzheimer's Disease regardless of discontinuation for any reason and regardless of initiation of rescue intervention or change in background intervention in the entire study population regardless of tau level. Additionally, the same clinical question will be addressed in participants with early symptomatic Alzheimer's Disease and intermediate levels of tau proteins in the brain as measured by flortaucipir F18 PET scans.

The estimand is described by the following attributes:

[figure not shown]
Population: participants with early symptomatic Alzheimer's Disease.

Endpoint: Proportion of participants with complete brain amyloid plaque clearance as measured by florbetapir F18 PET scans

Treatment condition: the randomized treatment with or without change in background medication (treatment policy strategy).

Population-level summary: estimated odds of complete amyloid plaque clearance for donanemab versus aducanumab (odds ratio).

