4.4. Co-Primary Endpoints Analysis

The primary objectives of this study are to test the hypothesis that participants treated with donanemab will have a significantly greater proportion of participants who reach amyloid plaque clearance compared to participants treated with aducanumab at the 6-month timepoint in both the ITT population and the intermediate tau subpopulation.

As the 6-month timepoint is the first scheduled opportunity to collect a post-baseline florbetapir F18 PET scan, the comparison of donanemab to aducanumab in complete brain amyloid clearance at 6 months will be performed using logistic regression. The logistic regression model will include fixed effect for treatment, ApoE $\epsilon 4$ genotype, baseline amyloid level, and baseline age. The test for this endpoint will be based on the contrast for the main effect of treatment from this logistic regression model. This analysis will be conducted on the full ITT population and the intermediate tau subpopulation. In case of quasi-complete separation of data points which may be possible due to small sample sizes, a Firth's penalized logistic regression model will be used to make inference on treatment efficacy.

Treatment effects from these logistic regression models will be summarized using estimated probabilities within each treatment group, along with odds ratios and a 100*(1- α)% confidence intervals, where α is the two-sided significance level for the primary endpoints.

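### Protocol 9.1 defines the primary odds ratio from the two regimen-level clearance probabilities, but the planned logistic coefficient targets a covariate-conditional odds ratio, which lies further from 1 if the covariates are prognostic.

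*Protocol*

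**What the plan says.** Protocol 9.1 names two parameters of interest: "the probability that a participant will achieve complete brain amyloid clearance at 6 months under the donanemab treatment regimen" and "the probability that a participant will achieve complete brain amyloid clearance at 6 months under the aducanumab treatment regimen". It then writes OR_6m as the ratio of the odds formed from these two probabilities. SAP 1.1 gives the population-level summary of the co-primary estimand as "estimated odds of complete amyloid plaque clearance for donanemab versus aducanumab (odds ratio").

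On estimation, Protocol 9.1 says the odds ratio "will be estimated using logistic regression models as described in Section 9.3". Protocol 9.3.3 adjusts that model for ApoE e4 genotype and baseline amyloid, and says "Treatment effects will be presented using odds ratios and 95% confidence intervals". In SAP 4.4 the covariates besides treatment and genotype are "baseline amyloid level, and baseline age". On testing, SAP 4.4 says "The test for this endpoint will be based on the contrast for the main effect of treatment from this logistic regression model". Effects are to be "summarized using estimated probabilities within each treatment group, along with odds ratios", and a Firth penalised fit replaces the ordinary one under quasi-complete separation.

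Neither document calls the odds ratio marginal or conditional, gives a standardisation step, or says how the group probabilities are to be computed.

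**The concern.** The definition and the estimator point to different quantities. A formula with one probability per regimen is a marginal odds ratio. The exponentiated treatment coefficient of an adjusted logistic model is an odds ratio at fixed covariate values. The two differ even under perfect randomisation, because the odds ratio is non-collapsible: with a true effect and a prognostic covariate, the conditional value lies further from 1.

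There is reason to expect a prognostic covariate. SAP 4.4.1 defines clearance by an absolute threshold, below 24.1 centiloids, so the starting amyloid level bears directly on reaching it. Randomisation is also stratified on baseline amyloid.

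What is at stake is how the co-primary effect size and its interval are read. A reader who put properly averaged group probabilities into the protocol's formula would not recover the odds ratio printed beside them.

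**Working it through.** **Inputs from the documents**
- Planned 6-month clearance: 35.7% donanemab, 3.0% aducanumab (Protocol 9.5, SAP 5).
- About 90 evaluable per arm. About half of participants are expected to have intermediate tau, so about 45 evaluable per arm there (Protocol 9.5).
- Two-sided alpha 0.05; stated power at least 98% for each co-primary.

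**Input that is assumed.** The slope s is the change in log-odds of clearance per SD of a normally distributed prognostic score. The documents give no value, so a range is shown.

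**Step 1. Reproduce the stated power.** A pooled two-proportion z-test gives more than 99.99% at 90 per arm and 98.5% at 45 per arm. The stated 98% is reproduced.

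**Step 2. Marginal odds ratio from the protocol's formula.** (0.357/0.643) / (0.03/0.97) = 17.95. The risk difference is 35.7 − 3.0 = 32.7 points.

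**Step 3. Conditional odds ratio giving the same two rates.** For each s, solve for intercepts a_d and a_a so that expit(a + s·z), averaged over z ~ N(0,1), equals 0.357 and 0.03. The conditional odds ratio is exp(a_d − a_a).

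| s per SD | a_d | a_a | Conditional OR | Ratio to 17.95 |
|---|---|---|---|---|
| 0 | −0.588 | −3.476 | 17.95 | 1.00 |
| 0.25 | −0.597 | −3.505 | 18.3 | 1.02 |
| 0.5 | −0.622 | −3.593 | 19.5 | 1.09 |
| 1.0 | −0.710 | −3.930 | 25.0 | 1.39 |
| 1.5 | −0.829 | −4.448 | 37.3 | 2.08 |

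**Step 4. Why the averaging rule for the probabilities matters.** At s = 1, predictions at the covariate mean are expit(−0.710) = 33.0% and expit(−3.930) = 1.9%. Averaged over the covariate they are 35.7% and 3.0%. SAP 4.4 does not say which is meant.

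**Step 5. Compare with sampling error.** At the planned rates and 90 per arm, the unadjusted standard error of the log odds ratio is √(1/32.13 + 1/57.87 + 1/2.70 + 1/87.30) = 0.656. The 95% interval around 17.95 runs from about 5 to 65. At 45 per arm the standard error is 0.656 × √2 = 0.928, and the interval runs from about 3 to 111. Every conditional value in the table lies inside both.

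**Step 6. Finite-sample check.** Firth fits were simulated with 2,000 runs per scenario. The table gives the median coefficient OR and the median standardised OR from the same fits.

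| Per arm | s | Coefficient OR | Standardised OR |
|---|---|---|---|
| 90 | 0 | 16.4 | 16.2 |
| 90 | 1.0 | 22.9 | 16.1 |
| 90 | 1.5 | 34.1 | 16.3 |
| 45 | 0 | 14.8 | 14.6 |
| 45 | 1.0 | 21.0 | 14.6 |
| 45 | 1.5 | 31.2 | 14.8 |

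The gap appears within a single fit, while Firth shrinkage pulls both figures below their targets.

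**Step 7. The test.** Under the model, conditional OR = 1 exactly when marginal OR = 1. With no effect (4,000 runs per scenario, s of 1 and 2), the upper-tail rejection rate was 0.024 to 0.025 at 90 per arm and 0.016 to 0.019 at 45, against a nominal 0.025. Power of the adjusted Firth test at the planned rates was at least 98.7%.

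**The case against.** The strongest reply is that the marginal reading is inferred. Protocol 9.1 ties its odds ratio to the adjusted model in the same section, and the SAP's population-level heading names an estimand attribute without settling the type of odds ratio. Adjustment is clearly deliberate, since SAP 4.1 puts the stratification factors into the models. It is true that neither document uses either word. But the formula in Protocol 9.1 is explicit and contains no covariates, so the text needs reconciling whichever quantity was meant.

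A reader might go further and infer that the headline odds ratio will be substantially overstated. The documents do not support that, because they give no prognostic strength for any covariate. At a slope of 0.25 the gap is 2%, and at 0 there is none. The statement concerns the target and the same-fit comparison, not every estimate: when Firth is used and the covariates are weak, the median coefficient falls below 17.95.

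Nor is the odds ratio left to stand alone. SAP 4.4 already reports group probabilities beside it and provides for separation. What is missing is how those probabilities are averaged.

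The reply is also right that the remedy has limits. After a Firth fit the standardised odds ratio itself sits somewhat below the marginal value, and intervals are fragile with so few aducanumab clearances. These points shape the remedy but do not remove the need for it.

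**Conclusion.** The point holds as a mismatch between the protocol's formula and the quantity the model coefficient targets. Its size runs from nothing at a slope of 0 to about twofold at 1.5 per SD (17.95 against 37.3). That range rests on the planned rates, a normal prognostic score, a common treatment effect on the logit scale, and slopes that are assumptions.

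It concerns reporting and interpretation only. A reader might also infer that the co-primary test or the power claim is compromised. Neither is: under the model both odds ratios equal 1 together, the simulations showed no Type I inflation, the stated power reproduces, and the gating in SAP 2.1 depends on tests alone. The gap is also smaller than the uncertainty in the odds ratio itself. It is worth correcting because the correction is cheap and makes the reported effect agree with the protocol's own definition.

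**What to change.** In SAP 4.4:
- Keep the adjusted logistic test, with the Firth fallback.
- State that the group probabilities are obtained by predicting for every member of the analysis set under each regimen and averaging (g-computation).
- Report the marginal odds ratio and the risk difference from those averages.
- Label the exponentiated treatment coefficient as a conditional odds ratio.
- Pre-specify an interval method that works with sparse events, including after a Firth fit. With 45 per arm in the intermediate tau set, 45 × 0.03 = 1.35 aducanumab clearances are expected, and the chance of none is 0.97^45, about 25%. A plain delta-method or bootstrap interval may fail there.

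If the sponsor in fact intends a conditional odds ratio, Protocol 9.1 and SAP 1.1 should say so, and the averaging rule for the probabilities is still needed.

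The cost is a little programming. The stated odds ratio will be smaller if the covariates are prognostic, and the marginal interval may not agree exactly with the p-value from the conditional test, which the SAP should acknowledge. Design, sample size and alpha do not change.

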9.2. Analyses Sets

For the purposes of analysis, the following analysis sets are defined:

Participant Analysis Set	Description
Full analysis set / ITT analysis set	All randomized participants with baseline and at least one post-baseline amyloid PET scan. Participants will be included in the analyses according to the planned intervention.
Intermediate tau set	All randomized participants with baseline and at least one post-baseline amyloid PET scan and a baseline flortaucipir F18 PET scan meeting the intermediate tau criteria.

Participant Analysis Set	Description
Safety analysis set	All participants who are exposed to study intervention. Participants will be analyzed according to the intervention they actually received.

The full analysis and intermediate tau sets are used to analyze endpoints related to the amyloid plaque objectives and the safety analysis set is used to analyze the endpoints and assessments related to safety.

9.3. Statistical Analyses

9.3.1. General Considerations

Statistical analysis of this study will be the responsibility of the Sponsor or its designee.

Unless otherwise noted, tests of treatment effects will be conducted at a 2-sided alpha level of 0.05 (or equivalently, a 1-sided 0.025 alpha level); 2-sided CIs will be displayed with a 95% confidence level. All tests of interactions between treatment and other factors will be conducted at an alpha level of 0.05.

A suitable approach such as Bretz's graphical approach may be utilized to provide strong control of the study wise Type I error rate for the primary and key secondary hypotheses at an alpha level of 0.05 (Bretz et al. 2009; Bretz et al. 2011). Details on the graphical approach and testing strategy will be specified in the SAP prior to the first participant visit.

All amyloid plaque analyses will follow the ITT principle unless otherwise specified. An ITT analysis is an analysis of data by the groups to which participants are assigned by random allocation, even if the participant does not take the assigned treatment, does not receive the correct treatment, or otherwise does not follow the protocol.

When change from baseline is assessed, participants will be included in the analysis only if both a baseline and a postbaseline measure are available. Unless otherwise defined, a baseline measure is the last nonmissing observation collected prior to the first administration of study medications. Endpoint is the last nonmissing postbaseline measurement.

To allow for sequential testing, database locks and the testing of corresponding primary and key secondary objectives are expected to occur after all randomized participants have had a chance to complete the scheduled 24-week PET scan, the scheduled 52-week PET scan, and the scheduled 76-week PET scan. Data collected during the immunogenicity and safety follow-up period will be summarized and analyzed separately.

Any change to the data analysis methods described in the protocol will require an amendment only if it changes a principal feature of the protocol. Any other change to the data analysis methods described in the protocol, and the justification for making the change, will be described in the SAP and the clinical study report. Additional exploratory analyses of the data will be conducted as deemed appropriate.

The SAP will be finalized prior to first participant visit and it will include a more technical and detailed description of the statistical analyses described in this section. This section is a summary

of the planned statistical analyses of the most important endpoints including primary and key secondary endpoints.

9.3.1.1. Handling of Missing Data for Efficacy Endpoints

For most efficacy endpoints, participants will be included in the analysis only if baseline and at least one post-baseline measurement are available. For most endpoints analyzed after the 6 month database lock, participants will be included only if both baseline and post-baseline measurements are available. For analyses on endpoints at 12 or 18 months, only participants with baseline and at least one post-baseline measurements will be included and will be analyzed within the framework of the repeated measures models as detailed in the analyses. Sensitivity analyses for endpoints including last observation carried forward or other imputation-based techniques for handling missing data may be considered and will be detailed in the SAP.

